Appendix 2: Clinical Laboratory Evaluations

| Clinical Chemistry Panel (Fasted): | Hematology Panel: | Other Tests: | | | | |
|---|--|---|--|--|--|--|
| Alanine aminotransferase (ALT) Albumin Alkaline phosphatase (ALP) Amylase Aspartate aminotransferase (AST) Bilirubin (direct and total) Blood urea nitrogen Calcium Chloride Cholesterol Creatine kinase Creatinine Glucose Iron Lipase Magnesium Phosphorus Potassium Sodium Total protein Triglycerides Uric acid | Hematocrit Hemoglobin Mean corpuscular hemoglobin Mean corpuscular hemoglobin concentration Mean corpuscular volume Platelet count Red blood cell (RBC) count RBC distribution width White blood cell (WBC) count WBC differential (percent and absolute): Basophils Eosinophils Lymphocytes Monocytes Neutrophils | Hemoglobin A1c (HbA1c) ^b Thyroid-stimulating hormone (TSH) ^b Estimated glomerular filtration rate ^{a,d} SARS-CoV-2 (COVID-19) test Safety digoxin levels (serum) Coagulation Parameters: Partial thromboplastin time Prothrombin time International normalized ratio Serology ^b : Hepatitis B surface antigen (HBsAg) Hepatitis B virus (HBV) immunoglobulin M (IgM) core antibody Hepatitis C virus (HCV) antibody Human immunodeficiency virus (HIV) antibody | | | | |
| | Urinalysis: Bilirubin | For Female Subjects Only: Pregnancy test (qualitative serum or qualitative urine, quantitative serum human chorionic gonadotropin tests may be used | | | | |
| Urine Drug Screen ^a : Including but not limited to the following: Alcohol (ethanol) ^e Amphetamines Barbiturates Benzodiazepines Cannabinoids Cocaine (metabolite) Methadone Opiates Phencyclidine Cotinine | Color and appearance Glucose Ketones Leukocyte esterase Nitrite Occult blood pH and specific gravity Protein Urobilinogen Microscopic examination including bacteria, casts, crystals, epithelial cells, RBCs, and WBCs (if protein, leukocyte esterase, nitrite, or occult blood is positive) | for confirmation as needed and post-menopausal subjects may be eligible for participation if the results of the qualitative serum pregnancy or qualitative urine pregnancy test are positive but the quantitative serum human chorionic gonadotropin results are within the laboratory's reference ranges for post-menopausal women) ^c Follicle-stimulating hormone (post-menopausal female subjects only) ^b | | | | |

- a. Performed at Screening and Check-in (Day -1) only.
- b. Performed at Screening only.
- c. Performed at Screening, Check-in (Day -1), and Day 19 for End of Treatment (EOT) or Early Termination (ET) only.
- d. Calculated using the Chronic Kidney Disease Epidemiology Collaboration (CKD-EPI) equation.

e. Urine or breath test.

Appendix 3: Total Blood Volume

The following blood volumes will be withdrawn for each subject:

| Assessment | Approximate Blood Volume per Sample (mL) | Maximum Number of Blood Samples | Approximate Total Volume (mL) |
|---|--|------------------------------------|--|
| Serology | 8.0 | 1 | 8.0 |
| Hemoglobin A1c (HbA1c) | 4.0 | 1 | 4.0 |
| Digoxin pharmacokinetic (PK) sampling and future potential and/or exploratory analysis sampling | 4.0 | 50° | 200.0 |
| LOXO-305 PK and future potential and/or exploratory analysis sampling | 4.0 | | |
| Clinical laboratory evaluations: | | | |
| Hematology | 4.0 | 7 | 77.0 |
| Clinical chemistry ^b | 4.0 | 7 | 77.0 |
| Coagulation | 3.0 | 7 | |
| Digoxin safety samples ^c | 3.0 | 9 | 27.0 |
| Serum pregnancy test (female subjects only) | 4.0 | 3 | 12.0 |
| Serum follicle-stimulating hormone (post- menopausal female subjects only) | 4.0 | 1 | 4.0 |
| | | Total: | 332.0 mL |

^a At PK sampling timepoints where multiple analytes (ie, digoxin and LOXO-305) are assessed, a single blood sample will be taken for analysis (see Appendix 4).

If extra blood samples are required, the maximum blood volume to be withdrawn per subject will not exceed 500 mL.

^b Thyroid-stimulating hormone (TSH) and estimated glomerular filtration rate (eGFR) will be assessed as part of the clinical chemistry sample.

^c Serum concentrations of digoxin will be assessed as part of clinical laboratory evaluations on Days 7, 12, and 15.

Appendix 4: Schedule of Assessments

Covance Study: 8456071 Protocol Reference: LOXO-BTK-20021

| | Screening | | Treatment Period | | | | | | | | | | | | | Clinic Discharge EOT/ET ^w | Follow-up Phone Call (EOS) | | | | | | |
|--|---------------------|----------------------|------------------|---|---|---|---|---|----|----|----|----|----|----|----|--|-------------------------------|----|----|----|----|----|--|
| Study Procedures ^a | (Days -29 to -2) | Check-in (Day -1) | 1 | 2 | 3 | 4 | 5 | 6 | 7 | 8 | 9 | 10 | 11 | 12 | 13 | 14 | 15 | 16 | 17 | 18 | 19 | 20 | 7 (± 2) Days Post EOT/ET ^x |
| Confined to the CRU | | X | X | X | X | X | X | X | X | X | X | X | X | X | X | X | X | X | X | X | X | X | |
| Inclusion/Exclusion Criteria | X | X | | | | | | | | | | | | | | | | | | | | | |
| Informed Consent | X | | | | | | | | | | | | | | | | | | | | | | |
| Demographics | X | | | | | | | | | | | | | | | | | | | | | | |
| Medical History | X | Xb | | | | | | | | | | | | | | | | | | | | | |
| Height/Weight/BMI | X | Xc | | | | | | | | | | | | | | | | | | | | | |
| eGFR | X | X | | | | | | | | | | | | | | | | | | | | | |
| Physical Examination ^d | | X | | | | | | | | | | | | | | | | | | | | X | |
| 12-lead ECG ^e | X | X | X | X | X | X | X | X | X | X | | X | | X | | | X | X | | X | | X | |
| Vital Sign Measurementsf,g,h | X | X | X | X | X | X | X | X | X | X | | X | | X | | | X | X | | X | | X | |
| HDYF? Inquiry ⁱ | X | X | X | X | X | X | X | X | X | X | X | X | X | X | X | X | X | X | X | X | X | X | X |
| AEs/SAEs ^j | X | X | X | X | X | X | X | X | X | X | X | X | X | X | X | X | X | X | X | X | X | X | X |
| Digoxin Dosingk | | | X | X | X | X | X | X | X | X | X | X | X | X | X | X | X | X | | | | | |
| LOXO-305 Dosing ¹ | | | | | | | | | | X | X | X | X | X | X | X | X | X | | | | | |
| CC | | | | | | | | | | | | | | | | | | | | | | | |
| Clinical Laboratory Evaluations ^p | X | X | | | X | | | | X | | | | | X | | | X | | | | X | X | |
| Serum Digoxin Samples (for Safety | | | | | | | | | X | X | X | X | X | X | X | X | X | | | | | | |
| Monitoring) ^q | | | | | | | | | 71 | 71 | 71 | 71 | 71 | 71 | 21 | 21 | 21 | | | | | | |
| Hepatitis and HIV Screen | X | | | | | | | | | | | | | | | | | | | | | | |
| COVID-19 Test ^r | X | X | | | | | | | | | | | | | | | | | | | | | |
| HbA1c Test | X | | | | | | | | | | | | | | | | | | | | | | |
| Drug Screen ^s | X | X | | | | | | | | | | | | | | | | | | | | | |
| Prior and Concomitant Medications ^t | X | X | X | X | X | X | X | X | X | X | X | X | X | X | X | X | X | X | X | X | X | X | X |
| Serum Pregnancy Test ^u | X | X | _ | | | | | | | | | | | | | | | | | | X | X | |
| FSH Test ^v | X | | _ | | | | | | | | | | | | | | | | | | | | |

Covance Study: 8456071 Protocol Reference: LOXO-BTK-20021

| | Screening | | Treatment Period | | | | | | | | | | | | Clinic Discharge EOT/ET ^w | Follow-up Phone Call (EOS) | | | | | | |
|----------|---------------------|---|------------------|---|---|---|---|---|---|---|----|----|----|----|--|-------------------------------|----|----|----|----|----|--|
| | (Days -29 to -2) | 1 | 2 | 3 | 4 | 5 | 6 | 7 | 8 | 9 | 10 | 11 | 12 | 13 | 14 | 15 | 16 | 17 | 18 | 19 | 20 | 7 (± 2) Days Post EOT/ET ^x |
| TSH Test | X | | | | | | | | | | | | | | | | | | | | | |

Abbreviations: AE = adverse event; BMI = body mass index; BP = blood pressure; COVID-19 = SARS-CoV-2; CRF = Case Report Form; CRU = Clinical Research Unit; ECG = electrocardiogram; eGFR = estimated glomerular filtration rate; EOS = End of Study; EOT = End of Treatment; ET = Early Termination; FSH = follicle-stimulating hormone; HbA1c = hemoglobin A1c; HDYF? = How Do You Feel?; HIV = human immunodeficiency virus; ICF = Informed Consent Form; PK = pharmacokinetic; SAE = serious adverse event; TSH = thyroid-stimulating hormone; UA = urinalysis.

- a. For details on study procedures, see Section 7.
- b. Interim medical history only.
- c. Height collected at Screening only; BMI calculated based on Screening height.
- d. A complete physical examination will be performed at Check-in (Day -1). An abbreviated physical examination will be performed at Day 20 (EOT) or at ET.
- e. 12-lead ECGs will be obtained at Screening and Check-in (Day -1), Day 1 (predose and 2 hours postdose), once daily on Days 2 to 7 (predose), Day 8 (predose and 2 hours postdose), Days 10, 12, and 15 (predose), Day 16 (predose and 2 hours postdose), Day 18, and Day 20 (96 hours postdose on Day 16 [EOT]) or ET. 12-lead ECGs will be collected after the subject has rested in the supine position for at least 10 minutes. When scheduled at the same time as PK blood draws, 12-lead ECGs will be obtained prior to and as close as possible to having blood drawn. The allowed sampling window for 12-lead ECGs is ± 30 minutes from the nominal timepoint for all postdose 12-lead ECGs and no less than 10 minutes prior to dosing for predose 12-lead ECGs.
- f. Vital sign measurements (supine BP and pulse rate) will be obtained at Screening, Check-in (Day -1), Day 1 (predose and 2 hours postdose), once daily on Days 2 to 7 (predose), Day 8 (predose and 2 hours postdose), Days 10, 12, and 15 (predose), Day 16 (predose and 2 hours postdose), Day 18, and Day 20 (96 hours postdose on Day 16 [EOT]) or ET. Blood pressure and pulse rate will be measured using the same arm for each reading after the subject has been supine for at least 5 minutes. When scheduled at the same time as PK blood draws, vital sign measurements should be carried out prior to and as close as possible to having blood drawn. The allowed sampling window for vital sign measurements is ± 30 minutes from the nominal timepoint for all postdose vital sign measurements and no less than 10 minutes prior to dosing for predose vital sign measurements.
- g. Respiratory rate and body temperature will be obtained at Screening, Check-in (Day -1), and Day 20 (96 hours postdose on Day 16 [EOT]) or ET.
- h. Oxygen saturation will be measured via pulse oximetry at Screening, Check-in (Day -1), predose on Day 1, and Day 20 (96 hours postdose on Day 16 [EOT]) or ET. The allowed sampling window for oxygen saturation measurements is ± 30 minutes from the nominal timepoint for all postdose oxygen saturation measurements and no less than 10 minutes prior to dosing for predose oxygen saturation measurements.
- i. A HDYF? inquiry will be performed at Screening (after the ICF is signed), at Check-in (Day -1), at each postdose vital sign measurement, and at an appropriate time for all other days.
- j. Adverse events and SAEs will be collected beginning at informed consent. Adverse events will be recorded throughout the study (ie, from signing of the ICF until EOS, or until ET if the subject discontinues from the study and does not complete a follow-up phone call), either as subject medical history (if the event is reported as beginning prior to signing of the ICF or if the event occurs prior to study drug administration on Day 1 and is assessed as not related to study procedures by the Investigator [or designee]) or as AEs (if the event occurs after signing of the ICF but prior to study drug administration on Day 1 and is assessed by the Investigator [or designee]) as related to study procedures, or if the event occurs after study drug administration on Day 1 through EOT or ET regardless of relationship to study drug). From EOT or ET through EOS, only AEs assessed as related to study drug are to be recorded. All SAEs that develop from the time of ICF signing until EOS (or ET if the subject discontinues from the study and does not complete a follow-up phone call) are to be reported.
- k. On Day 1, oral doses of 0.25 mg digoxin BID (loading dose) will be administered once in the morning and evening. Subjects will be fasted for at least 2 hours predose and 1-hour postdose for the morning and evening dose. Water will be restricted for 1 hour prior to and 1 hour after dosing with the exception of water administered for dose administration. On Days 2 through 16, oral doses of 0.25 mg digoxin QD will be administered at the actual time of the Day 1 morning digoxin dose (± 1 hour). On Days 8 through 16, oral doses of 200 mg LOXO-305 QD will be coadministered with oral doses of 0.25 mg digoxin QD, at the actual time of the Day 1 morning digoxin dose (± 1 hour). LOXO-305 will be administered first, immediately followed by digoxin. On Days 2, 4 through 6, 9 through 11, 13, and 14, subjects will fast for at least 2 hours predose and 1-hour postdose. On Days 3, 12, and 15 where clinical laboratory evaluations are

Covance Study: 8456071 Protocol Reference: LOXO-BTK-20021

performed, subjects will fast for at least 8 hours predose and 1-hour postdose. On Days 7, 8, and 16, subjects will be fasted at least 10 hours predose and 2 hours postdose. Water will be restricted for 1 hour prior to and 1 hour after dosing with the exception of water administered for dose administration.

1. On Day 8 through Day 16, oral doses of 200 mg LOXO-305 QD will be coadministered with oral doses of 0.25 mg digoxin QD in the morning at the actual time of the Day 1 morning digoxin dose (± 1 hour). LOXO-305 will be administered first, immediately followed by digoxin. On Days 2, 4 through 6, 9 through 11, 13, and 14, subjects will fast for at least 2 hours predose and 1-hour postdose. On Days 3, 12, and 15 where clinical laboratory evaluations are performed, subjects will fast for at least 8 hours predose and 1-hour postdose. On Days 7, 8 and 16, subjects will be fasted at least 10 hours predose and 2 hours postdose. Water will be restricted for 1 hour prior to and 1 hour after dosing with the exception of water administered for dose administration.

- p. Clinical chemistry panel (fasted for at least 8 hours), coagulation parameters, hematology panel, and UA will be performed at Screening, Check-in (Day -1), Day 3 (48 hours postdose on Day 1), Day 7 (predose), Day 12 (predose), Day 15 (predose), and Day 19 (72 hours postdose on Day 16, if the subject completes the study [EOT]), or on the day of ET. At ET or the day before EOT (Day 19), subjects are not required to be fasted prior to clinical laboratory evaluations.
- q. Serum digoxin level samples for safety monitoring will be collected predose on Days 7 through 15 and at the discretion of the Investigator (or designee).
- r. Testing for COVID-19 will be conducted at a minimum at Screening and Check-in (Day -1). Testing for COVID-19 may also be conducted periodically during the subject's CRU confinement, at the discretion of the Investigator (or designee). Tests will be performed by rapid polymerase chain reaction or equivalent.
- s. Urine drug screen for selected drugs of abuse (including cotinine) and alcohol screen (urine or breath).
- t. Prior and concomitant medication administration will be recorded beginning at informed consent. In addition, all Investigator-approved prescription and over-the-counter medications taken by a subject within 14 days or 5 half-lives (if known), whichever is longer, prior to Day 1 will be recorded on the subject's electronic CRF.
- u. Female subjects only. Performed at Screening, Check-in (Day -1), and Day 19 (72 hours postdose on Day 16), if the subject completes the study (EOT) or on the day of ET.
- v. Post-menopausal female subjects only.
- w. End of Treatment is defined as when the subject is released from the CRU following completion of all assessments through Day 20. Early Termination is defined as when the subject is released from the CRU if the subject terminates the study early. Vital sign measurements, ECG, and abbreviated physical examination results are to be available for review by the Investigator (or designee) prior to subject release from the CRU on Day 20 (EOT) or ET. Clinical laboratory results (for clinical chemistry, hematology, coagulation, and UA) and serum pregnancy test results (female subjects only) are to be available for review by the Investigator (or designee) prior to subject release from the CRU at the EOT visit and prior to subject release from the CRU at the ET visit if available.
- x. To be conducted 7 days (± 2 days) following EOT or ET. End of Study is defined as when the subject is contacted by the CRU for a follow-up phone call 7 days (± 2 days) after the EOT visit or ET visit to determine if any SAE or study drug-related AE has occurred since the EOT or ET visit. All subjects who received LOXO-305 or digoxin (including subjects who are terminated early) will receive a follow-up phone call.

Covance Study: 8456071

y. Denotes predose sample collection only.

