3. INVESTIGATIONAL PLAN

3.1. Overall Study Design and Plan

This is a Phase 1, open-label, fixed-sequence DDI study to investigate the effect of single and multiple oral doses of LOXO-305 on the PK of multiple oral doses of digoxin (P-gp substrate) in healthy subjects.

On Day 1, subjects will be administered oral 0.25 mg digoxin BID (loading dose), once in the morning and evening. Subjects will be fasted for at least 2 hours predose and 1-hour postdose for the morning and evening dose.

On Days 2 through 16, oral doses of 0.25 mg digoxin QD will be administered (total of 17 consecutive doses) at the actual time of the Day 1 morning digoxin dose (± 1 hour). On Days 8 through 16 (9 consecutive doses), oral doses of 200 mg LOXO-305 QD will be coadministered with 0.25 mg digoxin QD, at the actual time of the Day 1 morning digoxin dose (± 1 hour). LOXO-305 will be administered first, immediately followed by digoxin. On Days 2, 4 through 6, 9 through 11, 13, and 14, subjects will fast for at least 2 hours predose and 1-hour postdose. On Days 3, 12, and 15 where clinical laboratory evaluations are performed, subjects will fast for at least 8 hours predose and 1-hour postdose. On Days 7, 8, and 16, subjects will be fasted at least 10 hours predose and 2 hours postdose. Blood and urine samples for concentrations of digoxin in plasma and urine and

Blood samples for concentrations of LOXO-305 and digoxin in plasma and

Urine samples for concentrations of digoxin and CCl

Samples collected for the analysis of plasma and urine concentrations of digoxin and for analysis of LOXO-305 in plasma may be stored and analyzed CCl

The schematic of the study design is displayed in Figure 3. The start of the study is defined as the date the first subject who is enrolled in the study signs an Informed Consent Form (ICF). Note that enrolled subjects are defined as those subjects who are assigned to receive a dose of study drug; this definition excludes screen failure subjects. Replacement subjects may be enrolled only if deemed necessary by the Sponsor.

[figure not shown]
Subjects who are determined to be screen failures are permitted to be re-screened if the Investigator (or designee), with agreement from the Sponsor, feels that the subject may meet eligibility criteria upon re-screen. Re-screened subjects will be provided a new subject number.

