4.2. Check-in Procedures (Day -1)

At Check-in (Day -1), subjects will report to the CRU and the following procedures will be performed:

- 1. Review of inclusion/exclusion criteria
- 2. Interim medical history, including concomitant medication(s)
- 3. Weight and BMI

- 4. Complete physical examination (Section 7.2.5)
- 5. 12-lead ECG measured after the subject has been resting in the supine position for at least 10 minutes (Section 7.2.4)
- 6. Vital sign measurements (including body temperature, respiratory rate, oxygen saturation, and supine BP and pulse rate [measured after the subject has been supine for at least 5 minutes]; Section 7.2.3)
- 7. HDYF? inquiry, AE, SAE, and concomitant medication evaluations (Section 7.2.1)
- 8. Clinical laboratory evaluations (Section 7.2.2; clinical chemistry panel [fasted at least 8 hours], coagulation parameters, hematology panel, and UA; Appendix 2)
- 9. Screen for COVID-19 via PCR test (or equivalent; Appendix 2)
- 10. Urine drug screen for selected drugs of abuse (including cotinine) and alcohol screen (breath or urine; Appendix 2)
- 11. eGFR calculated using the CKD-EPI equation (Appendix 2)
- 12. Serum pregnancy test (for female subjects only; Appendix 2)
- 13. Compliance with concomitant medications and exclusionary restrictions (Section 6)

For subjects to continue their participation in the study, the inclusion/exclusion criteria must continue to be met at Check-in (Day -1 [as appropriate; #1, Section 4.2]). In addition, continued compliance with concomitant medication and other restrictions will be verified.

The Sponsor will review medical history and all screening evaluations for potential subjects prior to Check-in (Day -1). Prior to dosing, the Sponsor will provide approval of subjects selected for enrollment by the Investigator (or designee).

Subjects who meet all the inclusion criteria and for whom none of the exclusion criteria apply will be eligible to be enrolled into the study. Safety evaluations may be repeated at the discretion of the Investigator (or designee) or Sponsor.

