7.2.2. Clinical Laboratory Evaluations

Clinical laboratory evaluations (clinical chemistry panel [fasted at least 8 hours; at ET or the day before EOT, subjects are not required to be fasted prior to clinical laboratory evaluations], coagulation parameters, hematology panel, TSH [Screening only], HbA1c [Screening only], eGFR [Screening and Check-in (Day -1)], and UA) will be collected at the timepoints specified in Appendix 4.

Screens for HCV antibody, HBsAg, HBV IgM core antibody, and HIV antibody will be performed at Screening.

Testing for COVID-19 via PCR (or equivalent) will be performed at the timepoints specified in Appendix 4. Testing for COVID-19 may also be conducted periodically during the subject's CRU confinement, at the discretion of the Investigator (or designee). Further details regarding COVID-19 testing (including procedures for subjects who test positive at any time throughout CRU confinement) are specified in a separate document.

A urine drug screen for selected drugs of abuse (including cotinine) and an alcohol screen (urine or breath) will be performed at Screening and repeated at Check-in (Day -1) for all subjects. A serum qualitative or urine qualitative pregnancy test (female subjects only [quantitative serum human chorionic gonadotropin tests may be used for confirmation as needed and post-menopausal subjects may be eligible for participation if the results of the qualitative serum pregnancy or qualitative urine pregnancy test are positive but the quantitative serum human chorionic gonadotropin results are within the laboratory's reference ranges for post-menopausal women]) and an FSH test (post-menopausal female subjects only) will be performed at the timepoints specified in Appendix 4.

The number of blood samples and total blood volume required for clinical laboratory evaluations are presented in Appendix 3. A list of the specific evaluations is in Appendix 2.

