8.1.2. Calculation of the Summary Statistics

For continuous data the following rules will be applied:

- Missing values will not be imputed, unless specifically stated otherwise.
- Unrounded data will be used in the calculation of summary statistics.
- If the number of subjects with valid observations (n) <3, summary statistics will not be calculated, with the exception of n, minimum, and maximum.
- In general, as ET data are not associated with any scheduled timepoint, they will be excluded from all calculations of summary statistics and statistical analyses. Exceptions may be made where justified.
- Postdose repeats and unscheduled assessments will not be included in calculations of summary statistics.

For categorical data the following rules will be applied:

• For ordered categorical data (eg, AE severity), all categories between the possible minimum and maximum categories will be included, even if n = 0 for a given category.

• For non-ordered categorical data (eg, race), only those categories for which there is at least 1 subject represented will be included; unless specifically stated otherwise.

• Missing values will not be imputed, unless specifically stated otherwise. A 'missing' category will be included for any parameter for which information is missing. This will ensure that the population size totals are consistent across different parameters.

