8.6.2. Clinical Laboratory Parameters

All clinical laboratory parameters and their changes from baseline will be listed; any value outside the clinical reference range will be flagged, and whether the out of range value was deemed clinically significant or not clinically significant will be indicated.

Summary tables by treatment and timepoint will be provided for clinical chemistry, hematology, and coagulation parameters, and their changes from baseline, as applicable.

Values recorded as $\langle x, \leq x, \rangle x$, or $\geq x$ will be displayed in the listings as recorded. For the derivation of listing flags, all calculations, $\langle x \rangle x$ and $\leq x \rangle x$ values will be set to x.

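### The planned Day 19 chemistry need not be fasted, yet it is summarised as change from a fasted baseline with no flag, so food effects may appear in that row

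*Protocol*

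**What the plan says.** Protocol Appendix 2 heads the chemistry panel as fasted; the panel includes glucose and triglycerides. Appendix 4, note p, schedules it at Screening, at Check-in and then as follows: "Day 3 (48 hours postdose on Day 1), Day 7 (predose), Day 12 (predose), Day 15 (predose), and Day 19 (72 hours postdose on Day", the last of these being counted from the Day 16 dose.

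The fasting rules for these samples are:

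- **Check-in (Day -1):** Protocol Section 4.2 lists "clinical chemistry panel [fasted at least 8 hours], coagulation parameters, hematology panel, and UA; Appendix 2".
- **Days 3, 12 and 15:** Protocol Section 3.1 states "On Days 3, 12, and 15 where clinical laboratory evaluations are performed, subjects will fast for at least 8 hours predose and 1-hour postdose".
- **Day 7:** the same section states "On Days 7, 8, and 16, subjects will be fasted at least 10 hours predose and 2 hours postdose".
- **Day 19 and ET:** note p states "At ET or the day before EOT (Day 19), subjects are not required to be fasted prior to clinical laboratory evaluations". Protocol Section 7.2.2 agrees: "at ET or the day before EOT, subjects are not required to be fasted prior to clinical laboratory evaluations".

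SAP Section 8.1.4 takes baseline as the last available value before the Day 1 dose, which for chemistry is normally the Check-in sample. SAP Section 8.6.2 states "Summary tables by treatment and timepoint will be provided for clinical chemistry, hematology, and coagulation parameters, and their changes from baseline", qualified by a closing phrase that limits this to what is applicable. SAP Section 8.1.2 treats ET data differently: "as ET data are not associated with any scheduled timepoint, they will be excluded from all calculations of summary statistics", with room for justified exceptions.

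**The concern.** The exemption covers two different situations. An ET visit is unplanned, so fasting may be impracticable, and its values generally stay out of the summaries. Day 19 is a planned sample in every completer, and its values do enter them. Subjects are confined to the unit, receive no drug that day and eat meals served by the unit, so the practical reason that fits ET does not carry over. The documents give no other reason.

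Day 19 is also the only scheduled chemistry after the last dose. It alone can show whether a change seen on Day 12 or 15 has persisted or resolved. If some subjects have eaten, a food-sensitive value on Day 19 cannot be read cleanly against the fasted Day 15 value or the fasted baseline.

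Two features of the plan make this harder to sort out afterwards. The SAP has no fasting flag or footnote for the laboratory tables. And under SAP Section 8.1.3 any extra laboratory value is unscheduled and is left out of post-dose calculations, so a fasted repeat that explained an odd Day 19 result would not replace it in the summary.

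**Working it through.** **Step 1: reproduce the plan's own count.** Note p gives Screening, Day -1 and Days 3, 7, 12, 15 and 19, which is 7 samples. Protocol Appendix 3 also gives 7 for chemistry. Its laboratory volume agrees: 7 × 4 + 7 × 4 + 7 × 3 = 77 mL for chemistry, hematology and coagulation. The timepoint list is therefore complete.

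**Step 2: set fasting status beside the treatment label.**

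| Timepoint | Safety label | Fasting rule |
|---|---|---|
| Day -1 | normally baseline | at least 8 h |
| Day 3 | digoxin alone | at least 8 h |
| Day 7 | digoxin alone | at least 10 h |
| Day 12 | LOXO-305 + digoxin | at least 8 h |
| Day 15 | LOXO-305 + digoxin | at least 8 h |
| Day 19 | LOXO-305 + digoxin (inferred) | not required |

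After baseline, 0 of 2 digoxin-alone timepoints and 1 of 3 later timepoints may be unfasted.

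The Day 19 label is an inference. SAP Table 1 offers only two safety treatments and none for the period after dosing. The rule in SAP Section 8.6.1 that assigns everything from Day 8 onward to the combination has no end date, but it is written for adverse events. No rule assigns laboratory timepoints to treatments.

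**Step 3: size of the shift.** Let d be the mean shift that food causes in an analyte and f the share of subjects who have eaten before the Day 19 draw. Both are assumptions, because the documents give neither. With a fasted baseline:

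- shift in the Day 19 mean change = f × d
- shift in the Day 12 and Day 15 mean changes = 0
- shift in the Day 3 and Day 7 mean changes = 0

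With the planned maximum of 16 completers, each fed subject adds d/16 = 0.0625d:

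| Fed on Day 19 | f | Shift in Day 19 mean change |
|---|---|---|
| 0 of 16 | 0 | 0 |
| 4 of 16 | 0.25 | 0.25d |
| 8 of 16 | 0.5 | 0.5d |
| 16 of 16 | 1 | d |

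If the three later timepoints were averaged, the shift would be f × d / 3, at most 0.33d. The SAP does not average them; it summarises each timepoint separately.

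**The case against.** The case on the other side is substantial, and most of it stands.

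- **The exemption is deliberate and consistent.** Note p and Section 7.2.2 agree, so there is no contradiction to resolve. This stands: the point is about design, not an error in the text.
- **Fasting is not required, but a meal is not required either.** The nominal time, 72 hours after a morning dose, is itself a morning draw, and many subjects may not have eaten. A reader might infer that food effects will show up as treatment changes. The documents do not support that: f may be 0, and no percentage can be put on the shift without outside figures for both f and d.
- **The treatment comparison survives.** A reader might also infer that the comparison of the combination with digoxin alone is compromised. It is not. Days 12 and 15 are fasted and on treatment, and compare directly with fasted Days 3 and 7.
- **The reach is narrow.** Only the chemistry panel carries a fasting rule, and only its food-sensitive analytes are affected. SAP Section 8.6.6 plans no inference on safety data. Protocol Section 2.2.2 names laboratory evaluations as a means of assessing safety, without defining a laboratory-change endpoint.
- **There are safeguards.** Out-of-range values are marked as clinically significant or not, and laboratory changes count as adverse events only if clinically significant. This limits false signals in individual subjects. It does not correct the Day 19 summary row or tell its reader who had eaten.
- **Day 19 mainly serves review before discharge.** Appendix 4, note w, does require laboratory results to be available before release. The same values still go into the change-from-baseline table, and no other scheduled chemistry follows the last dose.

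**Conclusion.** The point holds as a minor gap in interpretability. The Day 19 row of the chemistry change-from-baseline table may mix fed and fasted subjects against a fasted baseline, with a shift of f × d (between 0 and d) in food-sensitive analytes and nothing in the outputs to reveal it. Rows for Days 3, 7, 12 and 15 are unaffected, and so is the pharmacokinetic analysis.

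The conclusion rests on three assumptions: that some subjects eat before the Day 19 draw, that some analytes in the panel respond to food, and that Day 19 is tabulated under LOXO-305 + digoxin, the likely but unstated label. The third affects only how a shift would be attributed; the mismatch with baseline exists under any label.

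**What to change.** In Protocol Appendix 4, note p, and Protocol Section 7.2.2, limit the fasting exemption to ET, so that the planned Day 19 chemistry follows the same fast of at least 8 hours as the other scheduled samples. This takes two wording edits and no added visit, procedure or blood volume. The cost to subjects is a delayed breakfast on a day when they are already in the unit.

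If Day 19 stays exempt, amend SAP Section 8.6.2 so that Day 19 chemistry is marked in tables and listings as taken without a fasting requirement, and so that food-dependent analytes are compared between treatments on Days 12 and 15. That costs a footnote and a sentence. It makes the limitation visible, but it does not restore a clean post-treatment value.
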